### **8.2 Recording Adverse Events**

The investigator will record all adverse events, regardless of relationship to study product on the adverse event CRF. Standard medical terminology should be used when describing adverse events. Whenever possible a diagnosis should be made and recorded on the CRF rather than listing signs and symptoms. Intermittent adverse events can be recorded once. The anatomical location of the adverse event must be specified, when applicable, as well as whether the location is a treatment area. The following information should be recorded on the CRF:

1. Description
2. Start date
3. Stop date or date of death, ongoing, or unknown
4. Severity of the event (see [8.3.1: Severity](#) for details)
5. Study product use continued or not
6. Outcome of the event (recovered/resolved, recovered/resolved with sequelae, not recovered/not resolved, unknown, fatal)
7. Relationship to study product (see [8.3.2: Relationship to Study Product \(Causality\)](#) for details)
8. Indication of whether the event is serious (see [8.3.3: Seriousness](#) for details)
9. Actions taken including treatment with concomitant medication

### **8.3 Assessment of Adverse Events**

#### **8.3.1 Severity**

It is the investigator's responsibility to assess the severity of each adverse event. Descriptions of severity are as follows:

1. Mild: Awareness of sign or symptom, but easily tolerated. Not likely to interfere with normal activity or require medical attention.
2. Moderate: Discomfort enough to cause interference with usual activity. May require medical intervention.
3. Severe: Incapacitating such that normal activity is prevented. Likely requires medical intervention and/or close follow-up.

#### **8.3.2 Relationship to Study Product (Causality)**

It is the investigator's responsibility to assess the relationship between the study product and the adverse event. The degree of "relatedness" of the adverse event to the study product should be described using the following categories:

1. Not Related: The event is clearly due to extraneous causes (e.g., diseases, environment, etc.). Specify if known. Or, the event is most probably produced by other factors such as the subject's clinical state, therapeutic interventions or concomitant therapy and does not follow a known response pattern to the study product.
2. Possibly Related: The event is temporally related to study product use but can be explained by another etiology. Information on the effect of study product withdrawal may be lacking.
3. Probably Related: The event is temporally related to study product use and is consistent with known effects of the study product and/or improves upon withdrawal of the study product.
4. Definitely Related: The event follows a reasonable temporal sequence from the time of study product administration and/or follows a known response pattern to the study product, and could not have been produced by other factors such as the subject's clinical state, therapeutic intervention or concomitant therapy, and either occurs immediately following study product administration, or improves on stopping the product, or there is a positive reaction at the application site.

#### **8.3.3 Seriousness**

It is the investigator's responsibility to determine the "seriousness" of an adverse event. A serious adverse event (SAE) is any adverse event occurring at any dose that results in any of the following outcomes:

---

1. Death
2. Life-threatening (subject at immediate risk of death)
3. Inpatient hospitalization or prolongation of hospitalization
4. Results in persistent or significant disability/incapacity
5. Results in congenital anomaly/birth defect

Important medical events that may not result in death, are not life-threatening, or do not require hospitalization may be considered an SAE when, based upon appropriate medical judgment, they may jeopardize the subject and may require medical or surgical intervention to prevent one of the outcomes listed above. Examples of such medical events include allergic bronchospasm requiring intensive treatment in an emergency room or at home, blood dyscrasias or convulsions that do not result in inpatient hospitalization, or the development of drug dependency or drug abuse.

#### **8.4 Reporting Serious Adverse Events**

SAE information must be faxed or emailed within 24 hours of becoming aware of the event. The minimum *initial* information required to be reported on the Serious Adverse Event Form is: the protocol number, site number, subject number, subject initials, the event, the causality, the date of the event and the name and contact information (email, phone number) of the person reporting the event. This initial report should be promptly followed up with a *completed* Serious Adverse Event Form.

**Serious Adverse Events:** [name]., M.S.

[contact]

Email: [contact]

The initial information must include a causality assessment that is provided by the primary investigator or other medically qualified individual. The causality assessment can be amended as more information is available. Significant new information about ongoing SAEs should be reported promptly to the sponsor.

Serious adverse events will be evaluated by the Medical Monitor within 24 hours of receipt and plans for management and further reporting (i.e. FDA) determined.

#### **8.5 Discontinuation Due to an Adverse Event**

The sponsor must be notified within 5 days if any subject is withdrawn or discontinues study product use due to an adverse event if AE is related to the study product (see title page for contact information).

#### **8.6 Exposure *in utero* (Pregnancy)**

If a female subject becomes pregnant during the study, study product must be discontinued immediately and she must be followed through the pregnancy and delivery. The investigator should report the event to the sponsor immediately (see contact information on title page) and complete the Pregnancy Surveillance Form. The expected date of delivery or expected date of the end of the pregnancy should be included in this information. The investigator is instructed to

---

contact the subject every 3 months until the end of her pregnancy and report the outcome to the sponsor. Details of the pregnancy, delivery and health of the infant should be recorded on the Pregnancy Surveillance Form.

The following outcomes of pregnancy fall under the criteria for serious adverse events and should be reported as such: delivery complications prolonging hospitalization, spontaneous abortion, stillbirth, death of newborn baby, congenital anomaly, and anomaly in a miscarried fetus.

## **9 DATA HANDLING AND RECORD KEEPING**

### **9.1 Confidentiality**

Information about study subjects will be kept confidential and managed according to the requirements of the Health Insurance Portability and Accountability Act. This regulation requires a signed authorization informing the subject's legal guardian of the following:

- What protected health information (PHI) will be collected from subjects in this study
- Who will have access to that information and why
- Who will use or disclose that information
- The rights of a research subject's legal guardian to revoke the authorization for use/disclosure of subject's PHI
- Expiration of authorization

In the event that a subject's legal guardian revokes authorization to collect and use PHI, the investigator, by regulation, retains the ability to use all information collected prior to the revocation of authorization. For subjects that have revoked authorizations to collect and use PHI, attempts should be made to obtain permission to collect at least vital status (i.e. that the subject is alive) at the end of their scheduled study period.

### **9.2 Source Documents**

Investigators must keep accurate separate records (other than CRFs) of all subject visits which include all pertinent study related information including original signed/dated informed consent forms. Source documents for this study include all written records of study data. All study data must have a paper source document including investigator assessments.

### **9.3 Screening/Enrollment Log**

A subject Screening/Enrollment Log, noting reasons for screen failure where applicable, must be maintained for all subjects who are consented. The log should also include subject initials, screening date, subject number, randomization number, assigned product and date and time of randomization, where applicable.

### **9.4 Case Report Forms**

The study case report form (CRF) for the study is a paper document which will be completed by the sites. All data requested on the CRF must be recorded on source documentation. The CRF

---

cannot be the source document for any data. Detailed instructions and training for completing the CRF will be provided to the sites.

Study subjects are not to be identified by name on CRFs, but rather by coded identifiers (subject number and initials). The investigator or sub-investigator must review all CRF pages for each subject and approve the group of CRFs pages for each subject.

### **9.5 Data Capture**

Study data will be entered into and maintained in a 21 CFR Part 11 compliant database.

### **9.6 Archiving of Study Documentation**

The investigator must retain study records for 2 years following the date a marketing application is approved for the investigational product; or, if the application is not filed or is not approved, until 2 years after the investigation is discontinued and the FDA is notified.

The sponsor will inform the investigator, in writing, as to when these documents no longer need to be maintained.

All study documents, original source documents, correspondence, IRB documents, etc. are subject to sponsor and FDA inspection at any time.

## **10 MONITORING AND DATA QUALITY ASSURANCE**

Only persons who are appropriately trained and who have the scientific and clinical knowledge to adequately monitor the study will be selected for monitoring this study. The monitor must have at least one year previous experience in monitoring clinical studies. The monitor should be familiar with the etiology and signs and symptoms of psoriasis and the treatment options that are currently available.

Before study initiation, the investigator and site personnel will receive protocol training from the sponsor's representatives to ensure collection of accurate, consistent, complete and reliable data. This training will take place either at an Investigator Meeting or individually on-site.

During the course of the study, a monitor will make multiple site visits to check the progress of the study, review consent forms, review protocol compliance, assess drug accountability, and ensure that the study is being conducted according to the protocol and Good Clinical Practice. Any review of the subjects' original medical records will be performed in a manner to ensure that subject confidentiality is maintained. The investigator will ensure that the monitor or other compliance auditor is given access to all study-related documents and has adequate time and space to conduct the monitoring visit including availability of the investigator and site personnel to discuss findings.

Data capture methods will be designed to ensure accurate transfer of data to electronic media.

---

The sponsor's Quality Assurance representative will conduct QA audits randomly or if needed at 5-10% of the investigator sites.

## **11 STATISTICAL CONSIDERATIONS**

All statistical processing will be performed using SAS® unless otherwise stated. Descriptive statistics will be used to summarize the data. No inferential testing will be performed. All summaries will be performed on the safety population.

No interim analyses are planned.

No imputations will be made for missing data.

A Statistical Analysis Plan, describing all statistical analyses, will be provided as a separate document prior to database lock.

### **11.1 Sample Size**

Approximately 50 subjects will be randomized to the two treatment groups in a 1:1 ratio for 25 subjects per group. No statistical justification has been made for the sample size.

### **11.2 Analysis Data Set**

All summaries will be performed on the safety population. All subjects who receive at least one confirmed dose of study product and provide any post-baseline safety information will be included in the safety population. No imputation will be made for missing safety data.

### **11.3 Demographic and Baseline Data**

Subject demographic and Baseline characteristics will be summarized by treatment group for the safety population. For continuous variables (e.g., age, BSA), descriptive statistics including sample size N, mean, median, standard deviation, minimum, and maximum will be presented. For categorical variables (e.g., IGA), descriptive statistics including N, frequency count and percentages will be presented.

### **11.4 Efficacy Summary**

Descriptive statistics will be used to summarize IGA by treatment group and visit and will include sample size, frequency counts, and percentages.

### **11.5 Safety Summaries**

Descriptive statistics will be presented to summarize the safety data. Continuous variables will be summarized with sample size N, mean, median, standard deviation, minimum, and maximum. Categorical variables will be summarized with sample size N, frequency counts and percentages.

### **11.5.1 Extent of Exposure**

The extent of exposure to study product in both treatment groups will be summarized as the total number of applications and the total amount of study product used based on bottle weights. The amount of the last dose will be provided based on bottle weight before and after treatment.

### **11.5.2 Local Safety Evaluation**

Atrophy, telangiectasia, burning/stinging, pain, or itching will be summarized by treatment group and visit.

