## 1 INTRODUCTION

Promius Pharma, LLC has developed a new spray formulation of betamethasone dipropionate, DFD-01 - Betamethasone Dipropionate Spray, 0.05% (potency expressed as betamethasone), for the topical treatment of psoriasis. Betamethasone dipropionate is a synthetic, fluorinated corticosteroid.

Psoriasis is a multisystem disease with predominantly skin and joint manifestations. The major manifestation of psoriasis is inflammation of the skin characterized by disfiguring, scaling, and erythematous plaques that may be painful or pruritic. Psoriasis is a chronic disease that waxes and wanes during a patient's lifetime, is often modified by treatment initiation and cessation and has few spontaneous remissions ([Menter, 2008](#)).

Psoriasis affects 7.5 million or 2.2% of the USA population at an estimated cost of 11.25 billion dollars annually ([National Psoriasis Foundation](#)). The most common form of psoriasis is chronic plaque disease. This presents as well-defined red scaly plaques typically distributed over the scalp, lower back, and extensor aspects of the limbs. Clinical variants include guttate psoriasis, sebopsoriasis, and pustular forms of psoriasis. A minority of patients with psoriasis (7%) also develop a seronegative inflammatory arthritis. Microscopically, lesional skin shows increased proliferation and abnormal differentiation of keratinocytes, infiltration by activated T-helper lymphocytes and neutrophils, and activation of the cutaneous vasculature ([Mendonca, 2003](#)).

Approximately 80% of patients affected with psoriasis have mild to moderate disease. The majority of these patients can be treated with topical agents, which generally provide both good efficacy and safety. Topical agents are also used adjunctively for resistant lesions in patients with more extensive psoriasis who are being concurrently treated with either ultraviolet light or systemic medications. Treatment should be tailored to meet individual patient's needs. These needs vary depending on body location, characteristics of the psoriasis being treated including lesion thickness, degree of erythema, and amount of scaling, as well as patient preference. The choice of vehicle can alter the use and penetration of the medication ([Menter, 2009](#)).

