**7.5.2 Other Safety Assessments**

Other safety assessments include vital signs, local cutaneous safety evaluation of the treated skin, and adverse events (AEs). Vital signs (blood pressure, pulse) will be collected at each visit. Adverse events will be collected by spontaneous reports from subjects and legal guardian, either verbal or recorded in the subject diary, by directed questioning of subjects and legal guardian, and by observation (see [Section 8](#) for details about AEs).

At Visits 2 (Baseline) through the End of Treatment Visit, the investigator will assess local cutaneous safety by examining treated areas for clinically significant atrophy and telangiectasia that will be recorded on the CRF as present or absent. The investigator will also ask the subject if any burning/stinging, pain, or itching has occurred in the treated areas since the last visit (for Visit 2 in the last 2 weeks). Baseline assessments are made prior to first application.

Subsequent to the Baseline Visit, for each symptom reported by subjects and/or each clinically significant sign, the presence of the sign or symptom must be recorded as “Yes” even if severity is not worse than Baseline. An adverse event should be recorded if the severity is worse than Baseline.

For female subjects, urine pregnancy tests will be conducted at Screening, Baseline, and every subsequent visit. These tests will be conducted just prior to the ACTH stimulation test, as

---

appropriate. The test must have a sensitivity of at least 25 mIU/mL for human chorionic gonadotropin.

Adverse events, whether believed by the investigator to be related or unrelated to treatment, will be recorded on the CRF.

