Any medical condition that is present at the time of Screening or Baseline should be considered as medical history and reported on the medical history CRF and should not be reported as an adverse event except for adverse events observed at the Baseline Visit due to study procedures performed at the Screening Visit which should be reported (except for worsening of psoriasis). Anticipated day-to-day fluctuations of pre-existing conditions should not be reported as adverse

---

events. Unexpected worsening of pre-existing conditions should be reported as adverse events. The disease or condition being studied or expected progression, signs, or symptoms of the disease or condition being studied should not be reported as an adverse event unless more severe than expected.

All serious adverse events, all study-product-related adverse events and all adverse events leading to study product discontinuation must be followed until the clinical outcome is determined or until all attempts to determine resolution of the event are exhausted (“not recovered” is not an acceptable outcome for acute conditions). For other adverse events, the status at the last visit can be entered into the CRF.

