#### **11.5.6 Vital signs**

Changes from Baseline in vital signs (blood pressure, pulse) will be summarized by treatment group at each evaluation.

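### Section 11.5.2 reports the solicited local skin findings only as by-visit frequencies, which do not show new onset; a Baseline shift and new-onset table would

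*Combined protocol and SAP*

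**What the plan says.** Section 11.5.2 is a single sentence: "Atrophy, telangiectasia, burning/stinging, pain, or itching will be summarized by treatment group and visit". Section 11.5 fixes the statistic: "Categorical variables will be summarized with sample size N, frequency counts and percentages". Neither section mentions a shift table, a new-onset rate or a count of subjects ever affected.

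Section 7.5.2 describes the data. The investigator examines treated areas for "clinically significant atrophy and telangiectasia that will be recorded on the CRF as present or absent" and asks about burning/stinging, pain and itching. After Baseline, "the presence of the sign or symptom must be recorded as “Yes” even if severity is not worse than Baseline". The same section, and Section 8, call for an adverse event when severity exceeds the Baseline level. Section 11.5.5 tabulates treatment-emergent adverse events by arm, number of subjects, preferred term, severity and relationship.

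Three other places bear on the point:
- The Introduction describes the disease as "disfiguring, scaling, and erythematous plaques that may be painful or pruritic". It also puts burning and itching first in its list of local reactions to topical corticosteroids.
- Section 8 states that "symptoms of the disease or condition being studied should not be reported as an adverse event unless more severe than expected".
- Section 11.5.6 does plan a Baseline comparison for another safety variable: "Changes from Baseline in vital signs (blood pressure, pulse) will be summarized by treatment group at each evaluation".

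**The concern.** Itching and pain can come from the disease, and itching is also a listed reaction to the drug class. If the product works, disease symptoms fall. If it irritates, new symptoms appear in other subjects. A by-visit percentage shows only the balance of the two, and because carried-over findings count as present, nothing in it marks which cases are new.

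Both arms receive the same active spray and differ only in duration, so a comparison between arms does not separate these components. Each subject's own Baseline record is the natural reference. It is already collected, but Section 11.5.2 does not use it at subject level.

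A second gap applies to all five items. Separate visit counts do not say whether the same subjects are affected each time, so they do not give the number ever newly affected during treatment.

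**Working it through.** The plan states no expected local-reaction rate, so there is no figure of its own to reproduce. The check asks what the planned table can and cannot determine.

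**Inputs.** n = 25 per arm (Sections 6.4 and 11.1: 50 subjects at 1:1, 50/2 = 25). Post-Baseline assessments are at Days 8, 15 and 29 in the 29-day arm and Days 8 and 15 in the 15-day arm (study schedules). All counts below are illustrative and assume complete data.

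**1. New onset between Baseline and one visit.** Let b subjects have the item at Baseline and v at the visit. Then

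v = b − resolved + new.

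With only b and v known, new onset lies between max(0, v − b) and min(v, 25 − b).

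| b | v | Planned table shows | Possible new onset | At risk (25 − b) | Rate among those at risk |
|---|---|---|---|---|---|
| 5 | 5 | 20% to 20% | 0 to 5 | 20 | 0 to 25% |
| 10 | 10 | 40% to 40% | 0 to 10 | 15 | 0 to 67% |
| 15 | 10 | 60% to 40% | 0 to 10 | 10 | 0 to 100% |
| 20 | 13 | 80% to 52% | 0 to 5 | 5 | 0 to 100% |
| 0 | 3 | 0% to 12% | exactly 3 | 25 | 12% |

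Take the third row. If 10 resolve and 5 are new, 15 − 10 + 5 = 10. If 5 resolve and none is new, 15 − 5 + 0 = 10. The planned table is the same in both cases. A shift table shows 5/10 new onset in the first (20% of the arm) and 0/10 in the second.

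The last row shows the limit of the problem. If nobody has the item at Baseline, the visit count is the new-onset count. This pattern is plausible for atrophy and telangiectasia, which the Introduction does not list as features of psoriasis.

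**2. How the balance depends on unknown rates.** Assume Baseline prevalence of 20, 40, 60 or 80%, resolution of 30, 50 or 70%, and new onset of 10, 30 or 50% among those at risk. The net change then runs from −54 points (80%, 70%, 10%: 20 × 0.3 + 5 × 0.1 = 6.5, or 26%) to +34 points (20%, 30%, 50%: 5 × 0.7 + 20 × 0.5 = 13.5, or 54%). It is negative in 22 of the 27 combinations with prevalence of 40% or more, and positive in 7 of the 9 at 20%. An apparent fall despite new reactions is thus mainly a risk for symptoms common at Baseline.

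**3. Subjects ever affected.** Suppose none has the item at Baseline and 2/25 have it at each of k later visits. The number ever affected lies between 2 (the same subjects each time) and 2k (different subjects each time):
- 29-day arm, k = 3: 2 to 6 subjects, 8% to 24%.
- 15-day arm, k = 2: 2 to 4 subjects, 8% to 16%.

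**4. The adverse event route beside the local data.** Sections 7.5.2 and 8 make a local item an adverse event if it is worse than Baseline. Section 7.5.2 specifies no severity grade for the five items, so the local data cannot confirm that judgement for a subject already affected at Baseline. Section 8 also keeps symptoms of the studied disease out of adverse event reporting unless they exceed expectation. New itch on a treated plaque could be handled under either instruction, and sites may differ. Section 8.2 records whether an event lies in a treatment area, but the Section 11.5.5 tables do not use that field.

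**The case against.** The strongest reply is that the plan already compares each subject with Baseline. Local items that worsen become adverse events, the investigator is told to watch atrophy and telangiectasia in particular, and Section 11.5.5 counts subjects by preferred term with severity and relationship. This stands in large part. A reader might infer that the plan contains no Baseline comparison at all, or that local harm would go unreported or appear as improvement. The documents do not support that: a worsened item has a route into the adverse event tables, and that route also covers worsening and causality, which a shift table does not.

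The disease-symptom rule can also be read narrowly. It concerns expected signs and symptoms, Section 8 keeps unexpected worsening of pre-existing conditions reportable, and the instruction on the five local items is more specific. That makes omission less certain, but it does not settle how new itch or pain on a plaque is to be classified.

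Three further replies have weight. The bounds hold for any pair of binary counts, and their upper ends are worst cases. The study is descriptive and its primary safety variable is the ACTH response. Section 11 announces a separate SAP, which is not in the material reviewed and might add such a table. These limit the importance; none shows that the by-visit summary identifies new onset.

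**Conclusion.** The point holds with limited scope. As written, Section 11.5.2 cannot distinguish new onset from the balance of onset and resolution for itching and pain, and possibly for burning/stinging, which the Introduction lists as a drug-class reaction (burning) but not as a disease symptom. For atrophy and telangiectasia this has little force if they are absent at Baseline; for them the remaining gap is the number ever affected.

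The size depends on Baseline frequencies that the documents do not give. With 10/25 at both times, new onset is anywhere from 0 to 10 of 15. With 2/25 at each visit and none at Baseline, 2 to 6 subjects (29-day arm) or 2 to 4 (15-day arm) are ever affected. These figures show what the table leaves undetermined and are not forecasts.

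The adverse event tables cover part of the gap, through an ungraded, open-label judgement and under two instructions in tension. This is an inexpensive improvement of modest importance to a secondary descriptive safety output.

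**What to change.** In Section 11.5.2 or the separate SAP, before database lock, add for each arm and each of the five items:

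1. a shift table of Baseline (absent/present) by each post-Baseline visit (absent/present);
2. the number and percentage with new onset at each visit, among subjects without the item at Baseline;
3. the number and percentage with new onset at any post-Baseline visit, with the same denominator.

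Keep the by-visit frequencies and read the new table alongside the treatment-emergent adverse event table. Section 11.5.8 plans no subset analyses, so state that the restricted denominator is part of the definition of new onset.

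Separately, the local-item instruction in Sections 7.5.2 and 8 and the disease-symptom rule in Section 8 must be reconciled, so that sites classify new or worsened itching and pain alike.

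State three limits with the table:
- It shows new onset, not worsening in subjects already affected at Baseline.
- It cannot by itself separate a drug reaction from a psoriasis flare.
- Symptom recall covers 14 days at Baseline but only about 7 days at Day 8 (8 − 1 = 7), which alone can lower the Day 8 frequency.

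The cost is one summary table from data already on the CRF and a clarification of the reporting text. No visits, assessments or subjects are added.
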